8.3. Assessment of other study variables

By recording demographic data as age, gender, height and weight, CPR experience (CPR course attendance, real live CPR experience) we will be able to investigate the influence of prior training, gender etc. on competences and decay of competences.

At the end of each course we will ask the participants how competent they feel on a visual analogue scale from 0 (totally incompetent, have no clue what to do) to 100 (totally competent, cannot be done better). The departmental research fellow will also rate the participant on the same scale.

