4.2 Outcomes

Our primary outcome will be the percentage of correct compressions obtained from the printed report from the LSR. With this parameter we will compare the two groups directly after the first teaching session.

Our secondary outcomes are:

- The subcomponents of the printed report from the LSR (ventilation volume, number of ventilations per minute, overall ventilation volume, number of ventilations, percentage of correct ventilations, number of ventilations with too much volume, number of ventilations with too little volume, number of ventilations that were too fast, the relation between ventilations and compressions, compression depth, number of compressions per minute, compression frequency, total number of compressions, percentage of correct compressions, number of compressions that were too deep, number of compressions that were too shallow, incorrect hand position, and incorrect decompression).
- The score on the BLS/AED provider assessment record(13) (fig.2).
- Degree of loss of competence after four months for all the primary and secondary outcomes.
- Influences of gender and prior BLS training will also be investigated, as well as the decay of competences.

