9. STATISTICAL METHODOLOGY

9.1. Determination of Sample Size

Based on a pilot study with 14 participants we calculated a median of 84% correct compressions. The interquartile range was 47% to 93%. We have discussed in the study group that a 20% decrease in percentage of correct compressions would have a clinically impact. Therefore, using a two-sample proportion test with a significance level α of 0.05 and an effect size of 20% (from 64% to 84%) we calculate that it requires 150 subjects to reach a power of 80%. To compensate for drop-outs, we aim to include 200 participants in the study.

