9.2. Planned analysis

All data will be summarized for each individual and a summary of all study participants will be computed. Data will be presented as mean (SD) or %.

Parametric data will be compared by a Students-t test, non-parametric by Mann-Whitney-U test. A $p < 0.05$ is considered as statistically significant.

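### Section 9.2 offers only two-group tests for a listed question, the influence of gender, prior training and other characteristics on skill and its decay, which needs an exploratory regression

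*Combined protocol and SAP*

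**What the plan says.** Section 4.2 closes its list of secondary outcomes with this item: "Influences of gender and prior BLS training will also be investigated, as well as the decay of competences". Section 8.3 lists what is recorded for the purpose: age, gender, height, weight, CPR course attendance and real-life CPR experience. It then says that with these data "we will be able to investigate the influence of prior training, gender etc. on competences and decay of competences".

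Section 9.2 is the whole analysis plan. Apart from summaries and a 0.05 threshold, it says: "Parametric data will be compared by a Students-t test, non-parametric by Mann-Whitney-U test". It names no regression, no adjustment and no interaction test. Section 6.1 describes randomization in blocks of 10 and mentions no stratification by gender or prior training. Section 7.3 excludes students with professional BLS experience, so the prior training and experience that remain are of other kinds.

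**The concern.** Randomization protects the comparison of the two teaching methods. It does not protect a comparison of men with women, or of students with and without an earlier CPR course. Those groups may differ in the other recorded characteristics, and a two-group test attributes the combined difference to whichever factor defines the groups. Age, height and weight are continuous, and neither planned test can use them as such.

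At stake is the answer to a question that the protocol lists and collects data for. A reader told that prior training, or gender, matters for skill or its retention would not know whether the difference belongs to that factor or to something that goes with it. Section 11 presents the trial as a possible basis for wider self-training, so such statements may be used.

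**Working it through.** **1. The plan's own figure.** Section 9.1 plans "using a two-sample proportion test with a significance level α of 0.05" for 64% against 84% and 80% power. Taking the test as two-sided and the arms as equal (neither is stated), with mean proportion 0.74:

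n per arm = [1.960·√(2·0.74·0.26) + 0.842·√(0.64·0.36 + 0.84·0.16)]² / 0.20² = (1.216 + 0.508)² / 0.04 = 74.3, so 75 per arm and 150 in total.

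This matches the stated 150, and 150/0.75 = 200 matches the recruitment target. Nothing below changes either number.

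**2. What a two-group contrast picks up.** If two groups differ by *d* in a second characteristic whose slope on the outcome is *b*, the unadjusted contrast contains an extra *b·d*. Take gender and weight as the example. The documents give no slope, no weight difference and no gender split, so these are assumptions: 0.3 to 0.6 points per kg, 10 to 15 kg, and 100 students of each gender.

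- Extra difference: 0.3·10 = 3 points to 0.6·15 = 9 points.
- SD from the pilot interquartile range in 9.1, treated as normal: (93 − 47)/1.349 = 34.1.
- SE = 34.1·√(2/100) = 4.82.
- Chance of p < 0.05 from this component alone: 3/4.82 = 0.62 gives 0.095; 9/4.82 = 1.87 gives 0.46.

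**3. The same check by simulation (2,000 runs per setting).** The grouping factor has no effect of its own. The second characteristic differs between the groups by 1 to 2 within-group SDs and has a coefficient of 0.1 to 0.3 outcome SD per SD (all assumed).

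| | N = 150 | N = 200 |
|---|---|---|
| Two-group t-test | 10% to 95% | 10% to 99% |

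A linear model with both terms stayed at 4% to 7% across all settings. The mechanism is the same for any correlated pair, such as prior training and age; a smaller imbalance gives a smaller excess.

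**4. Power of an arm-by-factor interaction.** With overall signal 1.960 + 0.842 = 2.80 at N = 150 and a fraction *f* of students in one stratum, an interaction as large as the main effect has signal 2.80·√(f(1−f)). At N = 200 this is multiplied by √(200/150) = 1.155.

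| Split | N = 150 | N = 200 |
|---|---|---|
| 50:50 | 29% | 37% |
| 80:20 | 20% | 25% |

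If the SD is 34.1 and the arm difference 20 points, the overall signal is 20/(34.1·√(2/75)) = 3.59, and the same formula gives 30% to 55% over these settings.

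**5. Only if the arms were compared within subgroups.** With an identical arm effect in two equal halves and 80% overall power, each half has signal 2.80/√2 = 1.98 and power 0.508. Exactly one half is significant with probability 2·0.508·0.492 = 0.50. At N = 200 the figures are 0.628 and 0.47. Under the SD of 34.1 and a 20-point effect, the probability is 0.40 at N = 150 and 0.28 at N = 200. A valid interaction test would mislead in 5%.

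**The case against.** Several points against the concern are sound.

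- **No subgroup comparison of the arms is announced.** A reader might infer that the sponsor will test self-learning separately in men and women, or in trained and untrained students, and report that it suits only some. Sections 4.2 and 8.3 speak only of influence on competences and their decay, which most naturally means a main effect. Step 5 is therefore a caution, not a description of the plan.
- **No cut-points are announced.** A reader might infer that age, height and weight will be split at the median, which for a normal covariate keeps 2/π = 64% of the information (200 students acting like 127). No section says this. What can be said is that the named tests cannot use these variables as continuous.
- **An unadjusted gender contrast is not wrong in itself.** A reader might infer that it is confounded by body size. Body size may instead be a route by which gender affects compressions, and the unadjusted contrast then validly estimates the total difference. The 3 to 9 points in step 2 are the gap between two possible targets. They are an error only if the difference at fixed body size is meant, which the documents do not say.
- **The magnitudes rest on assumptions.** Their width (10% to 99%) shows that the size is not established, and the SD comes from a skewed pilot of 14.
- **The question is subordinate.** Section 8.2 leaves gender and prior training out of its secondary outcomes, and 8.3 places them under other variables.

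It could also be said that 9.2 does not tie its tests to this question, so the plan is silent rather than wrong. But these are the only methods named, and they cannot separate correlated characteristics, use continuous ones or test an arm-by-factor difference. That part of the concern stands.

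**Conclusion.** The concern holds in a limited form. The protocol lists a question about non-randomized, possibly correlated characteristics and names only methods that take one two-level factor at a time. Those methods cannot give a prior-training effect separated from age, gender and real CPR experience, and they cannot use continuous age, height or weight. A regression on data already collected is the better method, so this is more than a missing detail.

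The size cannot be established from the documents, and the figures in steps 2 and 3 illustrate the mechanism only. The interaction power of about 20% to 37% assumes 80% main-effect power at N = 150, between 150 and 200 students, and strata between 50:50 and 80:20. The documents do not support saying that the plan will produce false subgroup findings, that covariates will be dichotomized, or that the gender comparison is invalid. The randomized primary comparison and the 150 and 200 of section 9.1 are untouched.

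**What to change.** Add to section 9.2:

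- An exploratory linear model, with robust or bootstrap standard errors, for the percentage of correct compressions directly after training. Terms: arm, gender, prior CPR course, real CPR experience and continuous age.
- A parallel model for the four-month change, since decay is part of the listed question.
- The gender coefficient reported twice: without height and weight (total difference) and with both as continuous terms (difference at fixed body size).
- Coefficients with 95% confidence intervals.
- A conditional rule: any claim that the arm effect differs by gender or prior training rests on the arm-by-factor interaction with its interval, labelled exploratory, and not on separate subgroup p values.

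The cost is a few lines of text. All the variables are already collected, and recruitment, procedures and sample size do not change. The drawback is imprecision: the interaction estimates will seldom settle anything, and the text should say so.

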9. STATISTICAL METHODOLOGY

9.1. Determination of Sample Size

Based on a pilot study with 14 participants we calculated a median of 84% correct compressions. The interquartile range was 47% to 93%. We have discussed in the study group that a 20% decrease in percentage of correct compressions would have a clinically impact. Therefore, using a two-sample proportion test with a significance level α of 0.05 and an effect size of 20% (from 64% to 84%) we calculate that it requires 150 subjects to reach a power of 80%. To compensate for drop-outs, we aim to include 200 participants in the study.

9.2. Planned analysis

All data will be summarized for each individual and a summary of all study participants will be computed. Data will be presented as mean (SD) or %.

Parametric data will be compared by a Students-t test, non-parametric by Mann-Whitney-U test. A $p < 0.05$ is considered as statistically significant.

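### Section 9.2 names no primary test, no between-group estimate and no confidence interval, and summarises a strongly skewed primary outcome only by mean (SD)

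*Combined protocol and SAP*

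**What the plan says.** Section 4.2 defines the endpoint: "Our primary outcome will be the percentage of correct compressions obtained from the printed report from the LSR". It is one score per student, bounded at 0 and 100, compared between groups directly after training.

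Section 9.1 describes the pilot of 14 participants by median and quartiles: "we calculated a median of 84% correct compressions. The interquartile range was 47% to 93" per cent. It then sets the relevant difference, "a 20% decrease in percentage of correct compressions would have a clinically impact", and sizes the trial "using a two-sample proportion test with a significance level α of 0.05 and an effect size of 20% (from 64% to 84" per cent).

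Section 9.2 gives the whole analysis plan. The summary rule is "Data will be presented as mean (SD) or" %, where the percentage most naturally serves categorical data. The test rule is "Parametric data will be compared by a Students-t test, non-parametric by Mann-Whitney-U test". No test is attached to the primary outcome, and nothing says how a variable is classed as one kind or the other. No median (IQR), between-group estimate or confidence interval is planned, and no other section supplies them.

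**The concern.** The investigators summarised their own pilot by median and interquartile range, then planned mean (SD) as the only summary of the same variable in the trial. With a score this skewed, Mann-Whitney is the likely test. The report would then hold a p value from a rank test beside means that the test does not compare.

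The study asks whether self-learning gives the same skills as instructor-led learning (section 2), and section 1 speaks of self-learning not being inferior. Either question needs an estimate and an interval to set against the 20 points in section 9.1. A non-significant p value with two means and SDs cannot show that the difference is smaller than 20 points. In addition, because no primary test is named, the plan does not rule out choosing it after the results of both are known.

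**Working it through.** **Inputs.** Pilot median 84, quartiles 47 and 93, n = 14; relevant difference 20 points (84 to 64); alpha 0.05; power 80%; total N 150 (all section 9.1). Assumed because not stated: 1:1 allocation, a two-sided test, and the shape of the distribution beyond the quartiles.

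**1. The plan's sample size.** Two-proportion formula, pooled variance, no continuity correction:

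n per arm = [1.96 × √(2 × 0.74 × 0.26) + 0.8416 × √(0.64 × 0.36 + 0.84 × 0.16)]² / 0.20² = (1.216 + 0.508)² / 0.04 = 74.3, so 75 per arm and 150 in total.

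The stated figure reproduces and is not disputed here.

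**2. Skewness.** The lower quartile lies 84 - 47 = 37 points below the median; the upper lies 93 - 84 = 9 above it. Quartile (Bowley) coefficient = (93 + 47 - 2 × 84) / (93 - 47) = -28/46 = -0.61.

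**3. Mean against median.** The quartile approximation gives (47 + 84 + 93)/3 = 74.7. A piecewise-linear distribution through 0/47/84/93/100 has as its mean the average of the four interval midpoints: (23.5 + 65.5 + 88.5 + 96.5)/4 = 68.5. So the mean lies about 9 to 16 points below the median.

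**4. How a 20-point gap in medians looks in means.** Reference arm as in step 3 (mean 68.5). The other arm has median 64, with four assumed shapes (minimum/Q1/median/Q3/maximum):

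| Other arm | Mean | Gap in means |
|---|---|---|
| 0/47/64/93/100 | (23.5 + 55.5 + 78.5 + 96.5)/4 = 63.5 | 5.0 |
| 0/40/64/86/100 | (20 + 52 + 75 + 93)/4 = 60.0 | 8.5 |
| 0/27/64/93/100 | (13.5 + 45.5 + 78.5 + 96.5)/4 = 58.5 | 10.0 |
| 0/27/64/73/80 | (13.5 + 45.5 + 68.5 + 76.5)/4 = 51.0 | 17.5 |

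A beta distribution fitted to the pilot quartiles (fitted quartiles 48/82/97, mean 70) gives a gap in means of about 11.6 points for medians of 82 and 64. That is inside the same range, though its median gap is 18 points, not 20.

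**5. Does the choice of test matter?** Simulated trials at 75 per arm:

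- A Shapiro-Wilk test rejected normality in every trial with the pilot shape, so Mann-Whitney is the likely branch.
- With no difference between arms, each test rejected in about 5% to 6% of trials. Always taking the smaller of the two p values gave about 6% to 7%.
- The two tests disagreed on significance in about 2% to 18% of trials, depending on the alternative.
- Neither is always stronger. With the other arm at quartiles 40/64/86, power was 42% (t) and 56% (Mann-Whitney). At 27/64/93 it was 50% and 40%.

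**6. Does the Hodges-Lehmann estimate recover the median gap?** Not in general. Under the beta model (medians 82 and 64) it is about 9 points, further from 18 than the gap in means of about 11.6. It equals the difference in medians only when one distribution is a pure shift of the other, which a bounded skewed score rarely allows.

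**The case against.** The strongest reply is that section 9.2 is a brief conventional rule. It does not say the test is chosen after looking at the trial data, and with the skew known from the pilot Mann-Whitney is the predictable choice. The t test holds roughly its nominal error at 75 per arm, and even the worst use of the freedom costs only a point or two of type I error. All of that stands. A reader might infer that the t test is invalid here, or that the open choice seriously inflates false positives; the calculations support neither.

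A reader might also infer that the trial will report a mean difference that understates a median-based threshold by a fixed share, such as one third. The documents do not support that. Section 9.2 plans no mean difference; mean (SD) is a descriptive rule. Section 9.1 uses the median as the reference value for the 20 points, then treats the difference as one between proportions, so its scale is never stated. The ratio also depends on the assumed shape, as step 4 shows. The evidence of skew rests on 14 people.

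None of this supplies the missing elements. The t-test branch has no estimate or interval either, and a predictable test is still not a named one.

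**Conclusion.** The point holds as a gap in the analysis wording, worth correcting but not fatal. The plan names no primary test, plans no between-group estimate or confidence interval, and offers no summary suited to a score with quartile skewness of -0.61. Followed as written, it probably yields a rank-test p value beside means and nothing to set against the 20 points.

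The size of any mismatch cannot be fixed from the documents. With piecewise-linear shapes and assumed tails, a 20-point gap in medians appears as about 5 to 17.5 points in means. The conclusion assumes that the trial data resemble the pilot, which makes Mann-Whitney likely rather than certain. Sizing a continuous score with a test for proportions is a separate question, and the arithmetic of N = 150 is correct.

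**What to change.** In section 9.2, before data are seen:

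- Name one test for the primary outcome and remove the open choice for that outcome.
- Report the primary outcome and other skewed LSR variables as median (IQR), with mean (SD) as an extra.
- State the scale on which the 20 points is defined, and give a between-group estimate with 95% CI on that scale. If it is anchored on the pilot median, use the difference in medians with a bootstrap 95% CI.
- If Mann-Whitney is the test, a Hodges-Lehmann estimate may accompany it, but it should not be read against a 20-point difference in medians.

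The cost is plan wording and a little more analysis work; data collection and sample size are unchanged. The drawback is that a difference in medians may be less precise than a difference in means.

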2. AIM OF STUDY

The aim of this study is to investigate whether self-learning versus instructor-led learning results in the same BLS skills in first year medical students directly after training and four months later.

¹ <http://www.laerdal.com/gb/MiniAnne#/Info>

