6. METHODS OF MINIMISING BIAS

6.1. Randomization

We will use a computerized randomization list (www.randomization.com) using block randomization of 10 to assure proper distribution during each group of students.

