7.3. Exclusion criteria

Students with professional BLS-experience, unable to perform BLS, or missing informed consent will be excluded.

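### Section 9.2 plans an unadjusted test but no between-arm difference with a confidence interval, so a non-significant result could not support a conclusion of same skills; an adjusted interval is a cheap addition

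*Combined protocol and SAP*

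**What the plan says.** The aim in Section 2 is to investigate whether "self-learning versus instructor-led learning results in the same BLS skills in first year medical students". Section 3 sets this up as a null of equal skills against an alternative of a difference. The Introduction words the null as non-inferiority of self-learning, and no margin appears anywhere.

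Section 9.2 is the whole analysis plan. The arm comparison is "Parametric data will be compared by a Students-t test, non-parametric by Mann-Whitney-U test", at p < 0.05. For reporting, "Data will be presented as mean (SD) or" percentages. No effect estimate, interval, model or covariate is named.

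Three other sections bear on what an analysis could use:

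- Section 6.1 uses "block randomization of 10 to assure proper distribution during each group of students". I read those groups as course sessions. The text does not say so, and it does not state stratification.
- Section 4.2 lists among the secondary outcomes: "Influences of gender and prior BLS training will also be investigated, as well as the decay of competences". Section 8.3 collects the data for this: "By recording demographic data as age, gender, height and weight, CPR experience (CPR course attendance, real live CPR experience". Section 9.2 gives no method for it.
- Section 7.3 narrows the range of prior training: "Students with professional BLS-experience, unable to perform BLS, or missing informed consent will be excluded".

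**The concern.** The result the trial hopes for is that self-learning is as good as instructor-led training. Section 11 says that equal, maintained skills would be a foundation for more self-training. If the test is non-significant, Section 9.2 as written leaves the reader with two means, two SDs and a p-value above 0.05. That does not say how large a deficit is still plausible. A confidence interval does, and a narrower one says it better.

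Two smaller gaps sit beside this. The blocking is meant to balance the arms within each group of students, and gender and CPR experience are recorded, yet none of this enters the comparison. A named secondary question, the influence of gender and prior training, has no analysis at all.

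**Working it through.** **1. The plan's own figure.** Section 9.1 sizes the trial on "an effect size of 20% (from 64% to 84"%), two-sided alpha 0.05 and 80% power. With pooled variance and no continuity correction, n per arm = [1.960·√(2·0.74·0.26) + 0.842·√(0.64·0.36 + 0.84·0.16)]² / 0.20² = (1.216 + 0.508)² / 0.04 = 74.3. This rounds up to 75 per arm, 150 in total, as stated. 150/0.75 = 200 corresponds to an implied 25% drop-out. The point below does not rest on a sample-size error.

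**2. Spread of the outcome (approximated).** The pilot of 14 gave a median of 84 and quartiles of 47 and 93. Two readings:
- IQR/1.349 = 46/1.349 = 34.1 points.
- A piecewise-linear distribution through 0/47/84/93/100: mean 68.5, SD 29.7.

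**3. What a p-value alone would miss.** SE = SD·√(2/n), half-width = t·SE, and power from the noncentral t.

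| n per arm | SD | SE | 95% half-width | Power, 20 points | Non-significant at a true 10-point deficit |
|---|---|---|---|---|---|
| 75 | 29.7 | 4.85 | 9.58 | 98.4% | 46% |
| 75 | 34.1 | 5.57 | 11.00 | 94.6% | 57% |
| 100 | 29.7 | 4.20 | 8.28 | 99.7% | 34% |
| 100 | 34.1 | 4.82 | 9.51 | 98.5% | 46% |

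An illustration at 75 per arm and SD 34.1: an observed deficit of 10 points is non-significant by the t-test (10 < 11.00). Its interval runs from a deficit of 10 + 11.00 = 21.0 points to an advantage of 11.00 − 10 = 1.0 point, so it does not rule out a 20-point decrease. An observed difference of zero gives ±11.00, which does rule it out. The planned output would call both non-significant.

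**4. What adjustment adds.** The documents give no R², intraclass correlation (ICC) or number of course groups, so all are assumed: 150 analysed, 15 groups of 5 + 5, and two binary covariates, with R² and ICC set on a latent normal scale mapped to the distribution in step 2. The model has arm, 15 group terms and 2 covariates, so 150 − 18 = 132 degrees of freedom against 148 for the t-test. It uses HC2 standard errors. Results are from 10,000 simulated trials per setting with no true difference.

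| Group ICC | R² | Half-width, t-test | Half-width, adjusted | Rejection, t-test | Rejection, adjusted |
|---|---|---|---|---|---|
| 0 | 0 | 9.58 | 9.66 | 5.1% | 5.1% |
| 0 | 0.10 | 9.58 | 9.23 | 5.0% | 4.9% |
| 0 | 0.20 | 9.59 | 8.77 | 5.2% | 4.9% |
| 0.10 | 0.10 | 9.55 | 8.77 | 4.0% | 4.8% |

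At SD 34.1, in closed form (SE·√(1 − R²) with 132 df), the half-width goes from 11.00 to 10.45 (R² 0.10) or 9.85 (R² 0.20).

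In equivalent sample size, 150·((9.58/9.23)² − 1) ≈ 12 students and 150·((9.58/8.77)² − 1) ≈ 29 students. If nothing is explained, 9.66/9.58 = 1.008, about 1% wider.

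Power for 20 points rises only from 98.4% to 99.1% or 99.6% (SD 29.7), or from 94.6% to 96.4% or 97.9% (SD 34.1).

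**The case against.** The strongest reply is that nothing is broken. Students are randomised individually, the unadjusted test holds its level, and the target difference will be detected with or without covariates. This stands. Further points:

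- **Mann-Whitney is the likelier comparator.** The pilot is left-skewed, so Section 9.2 would probably use the rank test. In simulation (4,000 runs, R² 0.10, no group effect), power for about 10 points was 51.2% for the t-test, 54.0% for Mann-Whitney and 53.7% for the adjusted model. For about 15 points with R² 0 it was 81.8%, 84.1% and 81.0%. The adjusted model gains about 3 to 4 percentage points over Mann-Whitney only at R² 0.20, or with a group ICC of 0.10 added to R² 0.10. This stands: power is not a reason to adjust.
- **The gain is assumed.** A single first-year class without professional BLS experience may show little explained variance. The primary test is on the training day, so close to 200 may be analysed and the interval is then narrower anyway (8.28 to 9.51). Both stand.
- **Tutors.** Whether arm A students share tutors is not stated. If they do and tutors differ, group terms remove a conservatism that partly offsets the tutor effect. At an assumed group ICC of 0.10, tutor ICC of 0.05 and 15 tutors, false rejection was 6.5% for the adjusted model and 5.1% for the t-test. This is a reason to leave the primary p-value with the unadjusted test.
- **An unadjusted interval would answer most of the point.** True; if only one part is adopted, it should be the interval.

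Some readers might infer more: that ignoring the blocks makes the test biased, that the trial is underpowered, or that the sponsor will declare equality from p > 0.05. The documents support none of these. Ignoring a balanced blocking factor makes the test slightly conservative (4.0% in the last row of the second table). Power is high. No decision rule for declaring equality is written.

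**Conclusion.** The point holds as a cheap improvement to the plan, not as an error. As written, Section 9.2 yields no arm difference and no interval for a question about equal skills, and a true 10-point deficit would be non-significant about 46% to 57% of the time at 75 per arm. That range rests on SDs approximated from the quartiles of a 14-person pilot; at 100 per arm it is 34% to 46%.

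The adjustment is secondary. It would narrow the half-width by roughly 0.35 to 0.8 points at SD 29.7 under R² of 0.10 to 0.20, and would not change whether a 20-point difference is detected. The missing method for gender and prior training is a plain gap that does not depend on any assumption.

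It is tempting to treat the 20 points in Section 9.1 as a non-inferiority margin. The documents call it a decrease with clinical impact and use it for sizing; they never state it as a margin.

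**What to change.** In Section 9.2:

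1. Keep the planned unadjusted test and name it as the source of the primary p-value.
2. Add the between-arm difference in percentage of correct compressions with a 95% confidence interval, from a linear model on arm, prior CPR training and gender. Include course group if blocks are applied within course sessions and the session is recorded; Section 8.3 does not list it. Use HC2 or bootstrap standard errors, because the outcome is bounded and skewed.
3. Read the interval against the 20-point decrease in Section 9.1, and say that this is not a pre-stated non-inferiority margin.
4. For the question in Sections 4.2 and 8.3, report the main-effect associations of gender and prior training with the score and with its four-month change. Arm-by-covariate interactions answer a different question and should not be used for this.

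The cost is a few lines of text, a course-session entry per student and about 16 degrees of freedom (148 to 132 under the assumed 15 groups). The interval is about 1% wider if the covariates and course groups explain nothing. If arm A students share tutors, the adjusted interval may be mildly too narrow. The interval and a rank-test p-value can also disagree near the threshold, so the text should say that the test carries the p-value and the model the estimate. No extra participants or visits are needed.
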